APPENDIX 7. CASE REPORT FORMS

Case report form: follow-up day 0	
Health centre name: Locality(Village): District: Province:	Study number: Patient identity number: Date of visit (dd-mm-yyyy):
Demographic data	
Date of birth (dd-mm-yyyy):	or estimated age: in:  months or  years
Height (cm):	Weight (kg): Sex:  Male  Female
If female, is the patient pregnant?  Yes  No  Not sure (If yes, patient is not eligible).	
If pregnant, provide the date of the last menstrual period (dd-mm-yyyy):	
Pre-treatment temperature	
History of fever in previous 24 h?  Yes  No	
Temperature: °C  Axillary 1	
Thick blood smears for P. falciparum : quantitative parasite counts and qualitative gametocyte counts	
Average number of asexual P. falciparum parasites/ μ l:	
Presence of P. falciparum gametocytes?  Yes  No	
Were species other than P. falciparum present?  Yes  No (If yes, patient is not eligible).	
If yes, which species?  P. vivax  P. ovale  P. malariae	
Has blood sample for PCR been collected?  Yes  No	

Case report form: follow-up day 0 (page 2)				
Medication administration				
Name(s) of antimalarial drug(s)	Time of dose (hh:min)	Number of tablets	Did the patient vomit?	Time of vomiting (hh:min)
			 Yes  No	
			 Yes  No	

Name(s) of other medicine(s)				
			 Yes  No	
			 Yes  No	

Case report form: follow-up day 1

Study number:

Patient identity number:

Date of visit (dd-mm-yyyy):

Clinical status

Presence of danger signs or signs of severe or complicated malaria? Yes No

If yes, perform thick blood smear.

Temperature: °C Axillary

Thick blood smears for estimation of *P. falciparum* parasite counts

Average number of asexual *P. falciparum* parasites/μl:

Presence of *P. falciparum* gametocytes? Yes No

Were species other than *P. falciparum* present? Yes No

If yes, which species? *P. vivax* *P. ovale* *P. malariae*

Adverse events

Presence of an adverse event? Yes No

If yes, name the adverse event:

Is it a serious adverse event? Yes No. If yes, inform the sponsor.

Medication administration

Name(s) of antimalarial drug(s)	Time of dose (hh:min)	Number of tablets	Did the patient vomit?	Time of vomiting (hh:min)
			 Yes  No	
			 Yes  No	
Name(s) of other medicine(s)				
			 Yes  No	
			 Yes  No	

Case report form: follow-up day 2

Study number:

Patient identity number:

Date of visit (dd-mm-yyyy):

Clinical status

Presence of danger signs or signs of severe or complicated malaria? Yes No

Temperature: °C Axillary

Thick blood smears for estimation of *P. falciparum* parasite counts

Average number of asexual *P. falciparum* parasites/ μ l:

Presence of *P. falciparum* gametocytes? Yes No

Were species other than *P. falciparum* present? Yes No

If yes, which species? *P. vivax* *P. ovale* *P. malariae*

Adverse events

Presence of an adverse event? Yes No

If yes, name the adverse event:

Is it a serious adverse event? Yes No. If yes, inform the sponsor.

Medication administration

Name(s) of antimalarial drug(s)	Time of dose (hh:min)	Number of tablets	Did the patient vomit?	Time of vomiting (hh:min)
			 Yes  No	
			 Yes  No	
Name(s) of other medicine(s)				
			 Yes  No	
			 Yes  No	

Case report form: follow-up day 3

Study number:

Patient identity number:

Date of visit (dd-mm-yyyy):

Clinical status

Presence of danger signs or signs of severe or complicated malaria? Yes No

Temperature: °C Axillary

Thick blood smears for estimation of *P. falciparum* parasite counts

Average number of asexual *P. falciparum* parasites/μl:

Presence of *P. falciparum* gametocytes? Yes No

Were species other than *P. falciparum* present? Yes No

If yes, which species? *P. vivax* *P. ovale* *P. malariae*

Adverse events

Presence of an adverse event? Yes No

If yes, name the adverse event:

Is it a serious adverse event? Yes No. If yes, inform the sponsor.

Medication administration

Name(s) of antimalarial drug(s)	Time of dose (hh:min)	Number of tablets	Did the patient vomit?	Time of vomiting (hh:min)
			 Yes  No	
			 Yes  No	
Name(s) of other medicine(s)				
			 Yes  No	
			 Yes  No	

Case report form: follow-up day 7

Study number:

Patient identity number:

Date of visit (dd-mm-yyyy):

Clinical status

Presence of danger signs or signs of severe or complicated malaria? Yes No

History of fever within previous 24 h? Yes No

Temperature: °C Axillary

Thick blood smears for estimation of *P. falciparum* parasite counts

Average number of asexual *P. falciparum* parasites/ μ l:

Presence of *P. falciparum* gametocytes? Yes No

Were species other than *P. falciparum* present? Yes No

If yes, which species? *P. vivax* *P. ovale* *P. malariae*

Has a blood sample for PCR been collected? Yes No

Adverse events

Presence of an adverse event? Yes No

If yes, name the adverse event:

Is it a serious adverse event? Yes No. If yes, inform the sponsor.

Medication administration

Name(s) of antimalarial drug(s)	Time of dose (hh:min)	Number of tablets	Did the patient vomit?	Time of vomiting (hh:min)
			 Yes  No	
			 Yes  No	
Name(s) of other medicine(s)				
			 Yes  No	
			 Yes  No	

Case report form: follow-up day 14

Study number:

Patient identity number:

Date of visit (dd-mm-yyyy):

Clinical status

Presence of danger signs or signs of severe or complicated malaria? Yes No

History of fever within previous 24 h? Yes No

Temperature: °C Axillary

Thick blood smears for estimation of *P. falciparum* parasite counts

Average number of asexual *P. falciparum* parasites/μl:

Presence of *P. falciparum* gametocytes? Yes No

Were species other than *P. falciparum* present? Yes No

If yes, which species? *P. vivax* *P. ovale* *P. malariae*

Has a blood sample for PCR been collected? Yes No

Adverse events

Presence of an adverse event? Yes No

If yes, name the adverse event:

Is it a serious adverse event? Yes No. If yes, inform the sponsor.

Medication administration

Name(s) of antimalarial drug(s)	Time of dose (hh:min)	Number of tablets	Did the patient vomit?	Time of vomiting (hh:min)
			 Yes  No	
			 Yes  No	
Name(s) of other medicine(s)				
			 Yes  No	
			 Yes  No	

Case report form: follow-up day 21

Study number:

Patient identity number:

Date of visit (dd-mm-yyyy):

Clinical status

Presence of danger signs or signs of severe or complicated malaria? Yes No

History of fever within previous 24 h? Yes No

Temperature: °C Axillary

Thick blood smears for estimation of *P. falciparum* parasite counts

Average number of asexual *P. falciparum* parasites/ μ l:

Presence of *P. falciparum* gametocytes? Yes No

Were species other than *P. falciparum* present? Yes No

If yes, which species? *P. vivax* *P. ovale* *P. malariae*

Has a blood sample for PCR been collected? Yes No

Adverse events

Presence of an adverse event? Yes No

If yes, name the adverse event:

Is it a serious adverse event? Yes No. If yes, inform the sponsor.

Medication administration

Name(s) of antimalarial drug(s)	Time of dose (hh:min)	Number of tablets	Did the patient vomit?	Time of vomiting (hh:min)
			 Yes  No	
			 Yes  No	
Name(s) of other medicine(s)				
			 Yes  No	
			 Yes  No	

Case report form: day ___ (any other day that is not part of regular follow-up)				
Study number:				
Patient identity number:				
Date of visit (dd-mm-yyyy):				
Clinical status				
Presence of danger signs or signs of severe or complicated malaria?  Yes  No				
History of fever within previous 24 h?  Yes  No				
Temperature: °C  Axillary				
Thick blood smears for estimation of P. falciparum parasite counts				
Average number of asexual P. falciparum parasites/μl:				
Presence of P. falciparum gametocytes?  Yes  No				
Were species other than P. falciparum present?  Yes  No				
If yes, which species?  P. vivax  P. ovale  P. malariae				
Has a blood sample for PCR been collected?  Yes  No				
Adverse events				
Presence of an adverse event?  Yes  No				
If yes, name the adverse event:				
Is it a serious adverse event?  Yes  No. If yes, inform the sponsor.				
Medication administration				
Name(s) of antimalarial drug(s)	Time of dose (hh:min)	Number of tablets	Did the patient vomit?	Time of vomiting (hh:min)
			 Yes  No	
			 Yes  No	
Name(s) of other medicine(s)				
			 Yes  No	
			 Yes  No	

Case report form: follow-up day 28

Study number:

Patient identity number:

Date of visit (dd-mm-yyyy):

Clinical status

Presence of danger signs or signs of severe or complicated malaria? Yes No

History of fever within previous 24 h? Yes No

Temperature: °C Axillary

Thick blood smears for estimation of *P. falciparum* parasite counts

Average number of asexual *P. falciparum* parasites/ μ l:

Presence of *P. falciparum* gametocytes? Yes No

Were species other than *P. falciparum* present? Yes No

If yes, which species? *P. vivax* *P. ovale* *P. malariae*

Has a blood sample for PCR been collected? Yes No

Adverse events

Presence of an adverse event? Yes No

If yes, name the adverse event:

Is it a serious adverse event? Yes No. If yes, inform the sponsor.

Medication administration

Name(s) of antimalarial drug(s)	Time of dose (hh:min)	Number of tablets	Did the patient vomit?	Time of vomiting (hh:min)
			 Yes  No	
			 Yes  No	
Name(s) of other medicine(s)				
			 Yes  No	
			 Yes  No	

Case report form: follow-up day 35

Study number:

Patient identity number:

Date of visit (dd-mm-yyyy):

Clinical status

Presence of danger signs or signs of severe or complicated malaria? Yes No

History of fever within previous 24 h? Yes No

Temperature: °C Axillary

Thick blood smears for estimation of *P. falciparum* parasite counts

Average number of asexual *P. falciparum* parasites/ μ l:

Presence of *P. falciparum* gametocytes? Yes No

Were species other than *P. falciparum* present? Yes No

If yes, which species? *P. vivax* *P. ovale* *P. malariae*

Has a blood sample for PCR been collected? Yes No

Adverse events

Presence of an adverse event? Yes No

If yes, name the adverse event:

Is it a serious adverse event? Yes No. If yes, inform the sponsor.

Medication administration

Name(s) of antimalarial drug(s)	Time of dose (hh:min)	Number of tablets	Did the patient vomit?	Time of vomiting (hh:min)
			 Yes  No	
			 Yes  No	
Name(s) of other medicine(s)				
			 Yes  No	
			 Yes  No	

Case report form: follow-up day 42

Study number:

Patient identity number:

Date of visit (dd-mm-yyyy):

Clinical status

Presence of danger signs or signs of severe or complicated malaria? Yes No

History of fever within previous 24 h? Yes No

Temperature: °C Axillary

Thick blood smears for estimation of *P. falciparum* parasite counts

Average number of asexual *P. falciparum* parasites/μl:

Presence of *P. falciparum* gametocytes? Yes No

Were species other than *P. falciparum* present? Yes No

If yes, which species? *P. vivax* *P. ovale* *P. malariae*

Has a blood sample for PCR been collected? Yes No

Adverse events

Presence of an adverse event? Yes No

If yes, name the adverse event:

Is it a serious adverse event? Yes No. If yes, inform the sponsor.

Medication administration

Name(s) of antimalarial drug(s)	Time of dose (hh:min)	Number of tablets	Did the patient vomit?	Time of vomiting (hh:min)
			 Yes  No	
			 Yes  No	

Name(s) of other medicine(s)

			 Yes  No	
			 Yes  No	

Urinary analysis (pregnancy test for female patients)

Patients with a positive pregnancy test must be followed up for 6–8 weeks after delivery

Result of pregnancy test: Positive Negative Date of test (dd-mm-yyyy):

If the patient is pregnant, follow-up of the pregnancy is required, including: clinical examination of the infant at birth and 6-8 weeks after birth. Please provide comments below. If needed fill in the serious adverse event report form):

Case report form: final day of follow-up day 42

Overall assessment

Outcome:

- adequate clinical and parasitological response
- early treatment failure
- late clinical failure
- late parasitological failure
- lost to follow-up
- withdrawn (complete section below: Reason for withdrawal)

Outcome occurred on follow-up day: (e.g. 1, 2, 3, 7, 14, ...)

PCR:

- P. falciparum* recrudescence
- P. falciparum* reinfection
- other species
- mixed with *P. falciparum* recrudescence
- mixed with *P. falciparum* reinfection
- unknown

PCR corrected results:

- adequate clinical and parasitological response
- early treatment failure
- late clinical failure
- late parasitological failure
- lost to follow-up
- withdrawn

Reason for withdrawal:

Other comments:

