4. TREATMENT

4.1 Antimalarial treatment

ASMQ (Artesunate + Mefloquine co formulated).

The adult dose tablet contains 100mg Artesunate plus 220mg Mefloquine and the paediatric tablet contain 55mg Artesunate plus 55 mg Mefloquine. (Refer to Annex table for more detailed dosage).

ASP (Artesunate + Pyronaridine/ Pyramax): Adults and children \geq 20 kg (Refer to Annex table for more detailed dosage).

All doses of medicine will be administered under the supervision of a qualified member of the staff designated by the principal investigator. The study patients will be observed for 30 min after medicine administration for adverse reactions or vomiting. Any patient who vomits during this observation period will be re-treated with the same dose of medicine and observed for an additional 30 min. If the patient vomits again, he or she will be withdrawn and offered rescue therapy. The patients are recommended to stay at the health facility until they complete the treatment course for malaria infection.

All doses of medicine will be administered under the supervision of a qualified member of the staff designated by the principal investigator. The study patients will be observed for 30 min after medicine administration for adverse reactions or vomiting. Any patient who vomits during this observation period will be re-treated with the same dose of medicine and observed for an additional 30 min. If the patient vomits again, he or she will be withdrawn and offered rescue therapy. The patients are recommended to stay at the health facility until they complete the treatment course for malaria infection.

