5.1.2 Safety end-points

The incidence of any adverse event will be documented. All patients will be asked routinely about previous symptoms and about symptoms that have emerged since the previous follow-up visit. When clinically indicated, patients will be evaluated and treated appropriately. All adverse events will be recorded on the case report form. Serious adverse events (see definitions in 5.3) must be reported to the sponsor.

³ WHO. *Susceptibility of Plasmodium falciparum to antimalarial drugs. Report on global monitoring 1996–2004*. Geneva, World Health Organization, 2005 (WHO/HTM/MAL/2005.110) (<http://www.who.int/malaria/resistance>).

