5.3 Safety assessment

Safety will be assessed by recording the nature and incidence of adverse events and serious adverse events. Adverse events will be assessed by direct questioning. An adverse event is defined as any unfavorable, unintended sign, symptom, syndrome or disease that develops or worsens with the use of a medicinal product, regardless of whether it is related to the medicinal product. All adverse events must be recorded on the case report form.

A serious adverse event is defined as any untoward medical occurrence that at any dose:

- results in death, is life threatening;
- requires hospitalization or prolongation of hospitalization;
- results in a persistent or significant disability or incapacity; or

- is a congenital anomaly or birth defect.

‘Life-threatening’ means that the person was at immediate risk for death; it does not refer to a adverse event that might have caused death if it were more severe. ‘Persistent or significant disability or incapacity’ means that a person’s ability to carry out normal life functions is substantially disrupted.

All serious adverse events occurring during the study must be recorded and reported by the principal investigator to the sponsor, regardless of whether the principal investigator considers the events to be related to the investigated medicine.

The investigator will collect information on any women who become pregnant while participating in this study and will record the information on the appropriate form. The pregnant woman will also be followed to determine the outcome of the pregnancy. Generally, follow-up will be no longer than 6–8 weeks after the estimated delivery date. Any premature termination of pregnancy will be reported. While pregnancy itself is not considered an adverse event or a serious adverse event, any complication of pregnancy or elective termination for medical reasons will be recorded as an adverse event or a serious adverse event. A spontaneous abortion is always considered a serious adverse event and will be reported as such.

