8.2 Analysis of data

Standard WHO spreadsheet will be used for data management and analysis. Data will be analysed by two methods: the Kaplan-Meier method and per-protocol analysis. In addition to the reasons for withdrawal listed in section 3.8, patients will be considered withdrawn from the analysis if the PCR results are unclassifiable or if the results of PCR indicate that the failure is due to reinfection with *P. falciparum*.

The final analysis will include:

- a description of all patients screened and the distribution of reasons for non-inclusion in the study;
- a description of all the patients included in the study;
- the proportion of adverse events and serious adverse events in all the patients included in the study;
- the proportion of patients lost to follow-up or withdrawn, with 95% confidence intervals and a list of reasons for withdrawal;
- the cumulative incidence of success and failure rates at day 28 and 42, PCR-uncorrected and PCR-corrected; and
- the proportion of early treatment failure, late clinical failure, late parasitological failure and adequate clinical and parasitological response at day 28 and 42, with 95%

⁵ WHO/GMP. *Standardized data entry for therapeutic efficacy tests*. Geneva, World Health Organization (<http://www.who.int/malaria/resistance>).

confidence intervals, PCR-uncorrected and PCR-corrected.

Guidelines on calculating the cumulative success or failure rate, the proportion of adequate clinical and parasitological response and treatment failure are given in Appendix 9.

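### The day-0 case report form has no adverse-event block although the first dose is given and observed that day, so some non-serious first-dose reactions can drop out of the safety result

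*Protocol*

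**What the plan says.** Section 4.1 of the protocol sets the watch: "The study patients will be observed for 30 min after medicine administration for adverse reactions or vomiting". Section 5.3 sets the recording duty: "All adverse events must be recorded on the case report form". Section 5.1.2 repeats that duty and adds questioning at each visit: "All patients will be asked routinely about previous symptoms and about symptoms that have emerged since the previous follow-up visit". Section 8.2 lists the safety result as "the proportion of adverse events and serious adverse events in all the patients included in the study".

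Section 6.2 defines day 0 as the day of enrolment and first dose, and Appendix 6 shows test medicine on days 0, 1 and 2. In Appendix 7 the first page of the day-0 form ends with the PCR sample. The second page, headed "Case report form: follow-up day 0 (page 2", contains only the medication table, which asks "Did the patient vomit" for each medicine and takes the time of vomiting. The item "Presence of an adverse event" is on neither day-0 page. It appears on the forms for days 1, 2, 3, 7, 14, 21, 28, 35 and 42 and on the form for any other day.

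**The concern.** On one of the three dosing days, staff must observe the patient and record what they see, but the form has no field for any reaction other than vomiting. Nor does section 8.2 say whether vomiting ticked in a dosing table enters the adverse-event count.

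Adverse-event frequency is the only secondary endpoint in the synopsis, safety is part of the general objective, and the results are meant to inform national treatment guidelines. A field missing on the day of first exposure can lose events but cannot create them, so any error makes tolerability look better than it was. Patients who tolerate the first dose worst are also the most likely to leave before a form with the block is completed.

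**Working it through.** **Denominator.** Five sites × (60 *P. falciparum* + 60 *P. vivax*) = 5 × 120 = 600 patients, as the synopsis states. Each has one first dose, given on day 0.

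**Where a first-dose event can be recorded.** Taking each kind of event in turn:

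- *Vomiting.* Recorded on day 0 in the medication table, with its time. Nothing in 8.2 links that tick to the adverse-event count.
- *Serious event.* The serious adverse event report form (Appendix 8) has a follow-up-day entry, so day 0 is covered.
- *Event that stops treatment.* Section 3.8 requires it to be noted on a case report form, 4.3 requires intolerance to be recorded as the reason for discontinuation, the final form has a reason-for-withdrawal field, and 8.2 lists those reasons. These entries appear under withdrawals and are not tied to the adverse-event count.
- *Event treated with another medicine.* Section 4.2 requires the medicine to be recorded, and the day-0 form has rows for it. Those rows name the medicine, not the event.
- *Any other non-serious reaction, patient seen on day 1.* Can be entered in the day-1 block through the look-back question in 5.1.2. This replaces what staff saw on day 0 with what is recalled the next day. The block has no onset date, so the event cannot be tied to the first dose.
- *Any other non-serious reaction, patient withdrawn or lost before day 1.* There may be no form with an adverse-event field. A patient who vomits twice on day 0 is withdrawn (3.8, 4.1), and follow-up after withdrawal happens only where possible (3.8).

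The last two rows, with the unlinked vomiting tick, are the gap.

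**Direction.** Under 8.2 a patient in the last row still counts in the denominator of all included patients but adds nothing to the numerator. If such a patient were instead removed from both, a patient with an event would still be lost and the proportion would again be too low.

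**Size.** The protocol gives no rate of first-dose reactions, so both inputs are assumptions. Let *p* be the share of patients with a first-dose event and *m* the share of those events that never reach an adverse-event field. Patients with an event left out = 600 × *p* × *m*:

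- *p* = 2%, *m* = 10%: 600 × 0.02 × 0.10 = 1.2
- *p* = 2%, *m* = 100%: 12
- *p* = 5%, *m* = 50%: 600 × 0.05 × 0.50 = 15
- *p* = 10%, *m* = 10%: 6
- *p* = 10%, *m* = 100%: 60

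The range is about 1 to 60 patients, or 0.2 to 10 percentage points of 600. The top end needs every first-dose event to be lost, and also needs none of these patients to have another event that is recorded.

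**The case against.** The strongest reply is that little falls through. Day-0 vomiting is on the very page that lacks the block. Vomiting twice leads to withdrawal, and 8.2 reports withdrawals with confidence intervals and reasons. Section 5.1.2 makes day-1 questioning cover the time since the first dose, and 5.3 requires direct questioning. Section 4.1 recommends that patients stay at the facility until the course is finished; for those who do, the staff who saw the reaction may still be at hand on day 1. How a vomiting column feeds the adverse-event dataset is often left to a statistical analysis plan, which is not at hand here. No threshold or comparison in the protocol depends on the adverse-event proportion.

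Most of this stands, and it limits the point. It does not remove it. The stay is a recommendation. Withdrawal reasons are a separate output from the adverse-event proportion. An analysis plan can settle how vomiting ticks are counted, but it cannot recover a rash or dizziness that was never written down. The form is part of this protocol, and it does not meet the protocol's own recording rule.

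A reader might infer that the safety result misses first-dose harm altogether, since 600 of the 3 × 600 = 1800 planned doses fall on day 0. That fraction measures exposure, not missed events. Likewise, one can construct a case where a true 15% (90 of 600) is reported as 10% (60 of 600), but only by supposing that 30 first-dose events are all lost. The existing recording routes do not support that.

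**Conclusion.** The point holds in a limited form. The day-0 form conflicts with the duty to record all adverse events on the case report form, and it is the only visit form without the block. The loss is confined to non-serious first-dose reactions that depend on day-1 recall, and to patients withdrawn or lost before day 1 who still count in the denominator. Whether vomiting in the dosing table counts as an adverse event is left unstated.

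The bias can only understate the adverse-event proportion. Its size cannot be derived from the protocol; about 1 to 60 of 600 patients follows from the assumed ranges (2% to 10% with a first-dose event, 10% to 100% of these unrecorded), and the existing recording routes argue against the upper end. The efficacy results and the sample size are unaffected.

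A reader might also infer that every vomiting tick should count as an adverse event. The protocol does not support that. Section 5.3 requires an event to be new or worse with the medicine, so vomiting already present from malaria and no worse would not qualify, and the same column also serves the rows for other medicines.

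**What to change.** - *Day-0 form (Appendix 7).* After the medication table, add the same adverse-event block used on days 1 to 42, limited to events that begin or worsen after the first dose.
- *Section 8.2.* State that vomiting of study drug recorded in the dosing tables counts as an adverse event when it meets the section 5.3 definition, that is, when it is new or worse after dosing.

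The form change matters more, since data not collected cannot be recovered at analysis. The cost is one more block to complete on one form and one sentence of text, with no extra visit or procedure and no change to treatment. The reported adverse-event proportion may rise slightly.
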